The primary analysis is to assess between-group differences in alcohol use measures including drinks per drinking day (primary outcome measure), heavy drinking days, and drinking days using Generalized Estimation Equations (GEEs) analysis with a site effect as a cluster. GEE model has been used in a prescription drug abuse treatment study with multiple site adaptive design (Weiss et al., 2010).¹⁰⁶ Point estimates of the difference in the average of the number of drinks per drinking day between treatment groups and their corresponding 95% confidence intervals will be obtained. A similar analysis will be used to assess exploratory aims 1 (mood), 2 (side effects), and 3 (craving). Length of time in the study in weeks will be compared between groups using Cox proportional hazards regression (SAS Proc PHREG). Assessments only obtained at baseline and weeks 6 and 12 (e.g. GGT, AST, ALT and CDT levels) or baseline and week12 (e.g. cognitive assessments, neurosteroid and choline levels) will be analyzed using analysis of variance (ANOVA). The correlation between the reduction in alcohol use/alcohol craving and reduction in manic and depressive symptoms, and also improvement in cognitive outcomes, will be assessed using Pearson's or Spearman's correlation coefficient. To address exploratory aim 6) "Determine whether changes in alcohol craving, mood or cognition occur before or after changes in alcohol use." a panel model with lagged effects¹³⁴ will be used to analyze 12-week longitudinal data (SAS Proc Panel) in order to explore serial correlations between changes in alcohol use and depressive symptoms or cognitive outcomes with lagged effect (e.g. one week, two week). The panel model will be constructed for each alcohol use, alcohol craving, depressive and manic symptom, and cognitive outcome and test if change in alcohol use follows changes in craving, mood or cognition at subsequent visits and vice versa.

At each stage, a table will show the adverse events (categorized by seriousness, severity, and possible association with study drug) ordered by decreasing frequency for all patients. If appropriate, the incidence rate of adverse events will be compared by Fisher's Exact Test. Special attention will be given to those participants who have discontinued due to adverse events or experienced a serious adverse event. Exploratory analyses such as determining if baseline blood neurosteroid or choline levels predict response and whether changes in these levels are associated with clinical response will be conducted using a mixed model (SAS Proc GLIMMIX) with baseline blood neurosteroid and choline levels as fixed effects. In addition, subgroup analyses with respect to patient demographics and characteristics may be performed as deemed appropriate by the PI and/or biostatistician. Unless otherwise noted, tests of hypotheses are 2-sided and the nominal level of significance will be 0.05.

3.3.d. Dropouts: Retention is challenging in studies involving BPD/schizoaffective disorder and substance dependence. We have greatly improved our retention over the years by implementing 1) more frequent visits, 2) more frequent contact to remind participants of appointments, and 3) the use of a psychosocial platform. To minimize attrition, we will obtain multiple contact numbers, pay participants small sums at each visit, and to the extent possible have the same research coordinator and psychiatrist assess participants at each visit. In addition, data will be analyzed using an analysis that uses all of the available data and allows for missing data. We will also use a contingency management strategy in which participants are given small vouchers that increase in value with consecutive appointments attended and reset following a missed appointment. We included a similar strategy in a recently completed study in BPD and cocaine dependence (Dallas site) and observed substantial improvement in retention. We anticipate that, using the above approach and considering completion rates in both PI's studies, the proposed study will have a completion rate > 70%. Although we will make every effort to minimize missing visits and dropouts, dropouts and missing visits are common in longitudinal studies. Therefore, we will do comprehensive sensitivity analyses to investigate the consequences of incomplete observations in the analysis of repeated measurement data using local influence, pattern mixture models and multiple imputations.¹³⁵⁻¹³⁷

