A structured clinical interview for DSM-5 (SCID)¹¹³ will be performed to establish the diagnoses of bipolar I or II disorder or schizoaffective disorder, bipolar type and alcohol use disorder. Clinical Institute Withdrawal Assessment of Alcohol Use-Revised (CIWA-Ar)¹¹⁴ will be administered. Eligible participants will then be given the HRSD₁₇,¹¹⁵ IDS-SR₃₀,¹¹⁶⁻¹¹⁹ YMRS,¹²⁰ HRSA,¹²¹ Penn Alcohol Craving Scale¹²² (PACS), Short Index of Problems (SIP), and a urine drug screen. Safety and side effects will be assessed with the Systematic Assessment for Treatment Emergent Events (SAFTEE).¹²³ Recent alcohol use (and, if present, other substance use) will be assessed using the Timeline Followback (TLFB) method. Length of problem alcohol use will be assessed by asking "When did alcohol first start causing you problems?" Blood will be drawn for laboratory analyses including a complete blood count (CBC) and Comprehensive Metabolic Panel (includes a liver panel with AST, ALT as well as lipids and electrolytes), and GGT and carbohydrate-deficient transferrin (CDT) will be added at baseline (week 0) and weeks 6 and 12. Cognition, including the domains of memory, decision making, impulsivity, attention, and executive functioning will also be assessed at baseline and week 12. A physical examination will be performed and weight obtained. Women of childbearing potential will receive a urine pregnancy test at baseline, week 6, and week 12 and will be counseled about effective contraceptive methods. A psychiatrist (PI or Co-I) will assess participants at baseline and weekly follow-up visits and will participate in the informed consent process. The psychiatrist will also prescribe a mood stabilizer (Lithium Carbonate or Risperidone) if the participant is not already on a stable dose. If prescribed, Lithium will be started at 600 mg nightly and Risperidone will be started at 2 mg nightly and continued for 21 days prior to starting the study medication or placebo. Mood stabilizer levels will also be tested, per clinician judgement, to assure the participant's medication adherence. The active medication or placebo capsules will be initiated at baseline and increased weekly in weeks 1, 2 and 3 to achieve the target doses for citicoline (2000 mg/day) or pregnenolone (500 mg/day). The titration schedule is as follows:

Pregnenolone

Week 0	50mg BID
Week 1	100mg BID
Week 2	150mg BID
Weeks 3-12	250mg BID

Citicoline

Week 0	250mg BID
Week 1	500mg BID
Week 2	750mg BID

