The clinician version of the SCID is a brief structured interview for major Axis I disorders in DSM.¹¹³ The CIWA-Ar is a 10-item, clinician-rated scale with a range from 0-67 that assesses alcohol withdrawal symptoms.¹¹⁴ The HRSD₁₇ is an observer-rated measure of depressive symptomatology.¹¹⁵ The IDS-SR₃₀ is a 30-item self-report scale of depressive symptom severity.¹¹⁶⁻¹¹⁹ YMRS is an 11-item, observer-rated measure of manic symptoms.¹²⁰ The HRSA is a 14-item observer-rated assessment of anxiety symptoms.¹²¹ PACS is a 5-item. self-report measure that includes questions about alcohol craving.¹²² The Short Index of Problems (SIP) is a 15-item self-rated measure that assesses recent and lifetime alcohol-related problems. The SAFTEE is a 56-item self-rated scale assessing a variety of somatic symptoms. TLFB is a method for assessing recent drinking, in which participants retrospectively estimate daily alcohol consumption over a period of time ranging from 7 days to 24 months.^{111, 112} The Treatment Impressions Inventory (TII) is a survey about your feelings and impressions about medical treatment. The World Health Organization/University of California at Los Angeles Auditory-Verbal Learning Test (WHO-UCLA AVLT) is designed to test verbal learning and memory. The Golden Stroop Color Word Test measures ease with which a person shifts perceptual sets to conform to changing demands and suppresses habitual responses in favor of non-dominant ones.¹²⁴ Trail Making Test (TMT) Parts A and B are tests for executive functioning, attention, sequencing, visual search, and motor function, with mental sequencing additionally required for Part B.¹²⁴ Columbia Suicide Severity Rating Scale (CSSRS) is a structured interview and rating scale used to measure suicidal ideation. An exit survey to evaluate participant's perception of in-person vs. virtual visits will be administered at week 12 or the last study visit in the event of early discontinuation.

Table 2. Assessment Schedule

														Wk
												Wk	Wk	12
Instrument	BL1	BL2	Wk 1	Wk 2	Wk 3	Wk 4	Wk 5	Wk 6	Wk 7	Wk 8	Wk 9	10	11	Final

SCID	Х													
YMRS, HRSD17, CSSRS, TLFB, CIWA-Ar, UDS	х	х	х	х	х	х	х	х	х	х	х	х	х	х
HRSA IDS-SR30, PACS, SAFTEE		х	х	х	х	х	х	х	х	х	х	Х	х	х
CBC, metabolic panel including AST, ALT (+ GGT, CDT), UPT	х							х						х
Lipid panel	х													х
Neurosteroid and choline levels		х												Х
Optional genetics blood draw		Х												

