Psychiatrist assessment, vital signs, weight	х	(X)	х	х	х	х	х	х	х	х	х	Х	Х	х
Physical exam, TII	х	(X)												
WHO-UCLA AVLT, TMT A and B, Stroop, SIP		х												х
ММ		х	х	х	х	х	х	х	х	х	х	х	х	Х
Exit survey														Х

3.3.b.6. Raters: All research coordinators have extensive experience working with dual-diagnosis patients, and a Bachelor's or Master's degree in psychology, social work or related field. Persons acquiring data, or with any participant contact, will be blind to treatment group. To assure that these instruments are administered properly, raters will receive training on the SCID and mood assessments. We will perform group inter-rater reliability assessments annually. At the PIs (Brown) group's most recent inter-rater reliability assessment the research assistants and coordinators had an intraclass correlation coefficient (ICC) of 0.98 on both the HAMD and YMRS. As part of the startup meeting in Dallas, prior to participant enrollment, interrater reliability will be assessed on the mood measures. Additional trainings will be conducted annually via videoconferencing.

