3.3.b.7. Diagnosis: Accurate diagnosis is challenging in dual-diagnosis patients. We will obtain psychiatric diagnoses based on a SCID interview and a clinical interview by a psychiatrist. When available, collateral information from family members or medical records will be used, with the potential participant's consent, as additional diagnostic information. Discrepancies between the SCID information and the information obtained from clinical interview will be resolved through discussion between the investigator, research coordinator, and potential participant. The SCID will be the source of the final diagnosis but the findings will be modified based on new information from the clinical interview. We will use DSM-5 criteria to distinguish substance-induced mood disorders and psychotic symptoms from BPD and schizoaffective disorder (bipolar type). Specifically, in the interviews we look for periods with mood and psychotic symptoms during time periods without substance use. In some cases no periods without substance use can be identified beyond childhood. Thus, using DSM-5 criteria, if all of the mood or psychotic symptoms occurred within one month of substance intoxication or withdrawal, a diagnosis of BPD or schizoaffective disorder (bipolar type) cannot be made. We acknowledge that some of the potential participants probably have BPD or schizoaffective disorder with comorbid severe and persistent substance-related disorders. However, in the interest of the internal validity of the research study, these persons will be excluded.

3.3.b.8. General Medical Evaluation: At baseline, participants will receive a laboratory evaluation that includes electrolytes, liver panel, lipids and complete blood count as well as a physical examination. Women of childbearing potential receive a urine pregnancy test and birth control information. At week 6 and at exit, participants will receive a repeat of the lab evaluation and women of childbearing potential will again receive a urine pregnancy test.

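### Table 2 has no pregnancy test between screening and first dose for participants who need a 21-day mood-stabiliser lead-in, and it disagrees with section 3.3.b.1 on the GGT/CDT baseline visit

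*Combined protocol and SAP*

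**What the plan says.** Section 3.3.b.1 states that GGT and CDT "will be added at baseline (week 0) and weeks 6 and 12". It schedules the urine pregnancy test for women of childbearing potential at baseline, week 6 and week 12, without the week 0 label, and adds contraceptive counselling. The same section says "The active medication or placebo capsules will be initiated at baseline", and the titration schedule begins at week 0. Participants not already on a stable mood stabiliser are prescribed lithium or risperidone, "continued for 21 days prior to starting the study medication or placebo".

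Table 2 splits baseline into BL1 and BL2. The row "CBC, metabolic panel including AST, ALT (+ GGT, CDT), UPT" is marked at BL1, week 6 and week 12, and its BL2 cell is empty. The row "Neurosteroid and choline levels" is marked at BL2 and week 12, as is "WHO-UCLA AVLT, TMT A and B, Stroop, SIP". The row "YMRS, HRSD17, CSSRS, TLFB, CIWA-Ar, UDS", which contains the urine drug screen, is marked at every visit, including BL2.

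Section 3.3.b.8 says "At baseline, participants will receive a laboratory evaluation that includes electrolytes, liver panel, lipids and complete blood count as well as a physical examination". It repeats the laboratory evaluation and pregnancy test at week 6 and exit. It does not name GGT or CDT, and it does not say which baseline visit is meant. The Statistical Methods text in 3.3.c analyses GGT, AST, ALT and CDT together from baseline and weeks 6 and 12, again without naming the visit.

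Pregnancy is an exclusion under the vulnerable-populations criterion and a discontinuation criterion in 3.3.b.3. Oral contraceptives are excluded.

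**The concern.** The text and the table place the GGT/CDT baseline at what appear to be two different visits. For participants who need a lead-in, those visits appear to be at least three weeks apart.

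The pregnancy test shares the table row, so it inherits the same timing. This matters more than the biomarkers. If sites follow Table 2, a woman who conceives during the lead-in could be given study drug with no scheduled test to detect it before week 6, even though pregnancy is a reason not to enrol her and a reason to stop her.

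The biomarker issue is one of definition. Two sites need one schedule, and the analysis needs one named baseline.

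**Working it through.** The plan states no figure to reproduce on this point. The check is a reading of the schedule followed by date arithmetic.

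**Step 1: the table columns.** Table 2 has 14 visit columns: BL1, BL2 and weeks 1 to 12. Counting cells in the extracted table gives:

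| Row | Columns marked | Visits |
|---|---|---|
| Safety labs, GGT, CDT, pregnancy test | 1, 8, 14 | BL1, week 6, week 12 |
| Neurosteroids and choline | 2, 14 | BL2, week 12 |
| Cognition and SIP | 2, 14 | BL2, week 12 |
| Row containing the urine drug screen | all 14 | every visit |

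The later marks in the laboratory row fall exactly on the weeks 6 and 12 named in the text, so the column reading is sound. The table also uses a bracketed mark at BL2 for the psychiatrist-assessment and physical-examination rows. The laboratory row has no such mark, so its BL2 blank does not look like a formatting accident.

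**Step 2: which visit is which (inferred).**

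- BL2 as the dosing visit: the first Medical Management session and the baseline neurosteroid/choline draw are at BL2, and the next column is week 1.
- BL1 as the screening visit: the diagnostic interview is at BL1, 3.3.b.1 describes ineligibility as being found at Baseline 1, and the inclusion criteria tie the risperidone prescription to status at screening. The lead-in therefore starts at or after BL1.

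**Step 3: intervals for lead-in participants.** Let g be the days from BL1 to the lead-in prescription. The documents give no value for g. The minimum is 0, and 7 and 14 are assumed for illustration.

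- Age of the BL1 sample and pregnancy test at first dose = 21 + g
- BL1 to week 6 = 21 + g + 42
- BL1 to week 12 = 21 + g + 84

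| g (days) | Age at first dose | BL1 to week 6 | BL1 to week 12 |
|---|---|---|---|
| 0 (minimum) | 21 | 63 | 105 |
| 7 (assumed) | 28 | 70 | 112 |
| 14 (assumed) | 35 | 77 | 119 |

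Measured from week 0, as the GGT/CDT sentence implies, the intervals would be 0, 42 and 84 days.

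**Step 4: after the fix.** With a pregnancy test at BL2 before the first capsule, the last test is 0 days old at first dose. The next follows 42 days later, which matches the spacing the plan already accepts between weeks 6 and 12. What the fix removes is the untested lead-in of at least 21 days.

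**The case against.** The best reply is that this is loose wording. The protocol often uses baseline for the whole BL1/BL2 period: cognition is described as a baseline assessment and sits at BL2, while the laboratory work is also described as baseline and sits at BL1. The week 0 label may mean only pre-treatment. Text and table agree on three draws, with GGT and CDT added to the routine panel. This could well explain the GGT/CDT mismatch. It does not remove the need to name the visit, and it does not supply a pregnancy test after the lead-in.

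For the pregnancy test there is no direct contradiction. The text says only baseline, so the issue is a gap in the schedule. Contraceptive counselling is provided, but counselling does not detect a pregnancy. The protocol also refers to a Human Subjects section that is not among the supplied pages. A further safeguard could be there, so the gap is established only for the text available.

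The visit roles are inferred, and neither the BL1-to-BL2 interval nor the number of lead-in participants is given. Both limits stand.

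A reader might go further in three ways that the documents do not support:

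- **Bias or lost precision in the biomarker analyses.** The BL1 sample and the lead-in both precede randomised treatment in every arm, so an older baseline does not bias the between-arm comparison. Any precision loss would depend on correlations, a lead-in share and an analysis form that the plan does not give. The plan names only an ANOVA. No figure is justified.
- **A stale baseline for everyone.** The 21-day minimum applies only to lead-in participants. Nothing can be said about those already stable.
- **Blaming the whole 63 days on the table.** The last 42 days are the plan's ordinary six-week testing interval. Only the lead-in portion is at issue.

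**Conclusion.** The point holds as a schedule gap with a small safety consequence, together with a document inconsistency. If Table 2 is followed, lead-in participants begin study drug with a pregnancy test and a GGT/CDT baseline at least 21 days old, and the supplied text schedules no further pregnancy test until week 6.

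This rests on reading BL1 as screening and BL2 as the dosing visit. That reading is well supported but unstated. It also rests on no other safeguard existing in the Human Subjects section, which was not supplied. How many women are affected, and how often conception would occur in the lead-in, cannot be estimated from the documents.

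No bias or loss of precision is claimed. The between-arm comparisons and the Timeline Followback primary outcome are unaffected. The point is minor, and worth acting on because the remedy is specific and cheap.

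**What to change.** 1. In Table 2, add a urine pregnancy test at BL2, before the first dose, for women of childbearing potential who had a mood-stabiliser lead-in. Use the urine already collected at BL2 for the drug screen. Keep the BL1 test for eligibility. The cost is one extra urine test per such woman, with no extra visit or sample.

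2. State in 3.3.b.1 and Table 2 that BL2 is week 0.

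3. Make text and table agree on one baseline visit for GGT, CDT, AST and ALT together, and name it in the Statistical Methods text of 3.3.c. Either option works:
   - All four at BL1, with the week 0 label in 3.3.b.1 corrected. This is a text change only.
   - All four on the blood draw already scheduled at BL2 for neurosteroids and choline, keeping the BL1 panel for eligibility. This adds a repeat AST/ALT assay but no venepuncture.

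   Moving GGT and CDT alone to BL2 should be avoided, because it would separate them from the AST and ALT baseline with which they are analysed.

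The BL2 pregnancy test is needed whichever option is chosen in item 3.

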Among participants with alcohol use disorder (in addition to cocaine), and active alcohol use at baseline (n=14), potentially meaningful changes in alcohol use and craving were observed. Citicoline-treated patients had a significant decrease in alcohol craving based on a 0-100 mm visual analogue scale (-28.7±31.3, p=0.05) while the placebo-treated group showed a much smaller decrease in alcohol craving (-1.9±66.4, p=ns). Despite modest baseline values, alcohol use decreased by 0.9 ± 1.4 days/week in the citicoline group as compared to only 0.4 ± 0.9 days/week with placebo. Heavy drinking days decreased by 0.9 ± 2.1 (p=0.04) days with citicoline as compared to 0.0 ± 0.6 with placebo. Drinks per drinking day decreased by 2.4 ± 11.3 with citicoline and 0.8 ± 2.6 with placebo. In the alcohol use group, RAVLT delayed recall performance increased by 12.4 ± 12.9 points with citicoline (p=0.04), but decreased by 1.8 ± 3.5 points with placebo (Cohen's d = 1.5, large effect size). Significance: Findings suggest reductions in both cocaine and alcohol use with citicoline. Memory improved with citicoline, particularly in those with alcohol use. Citicoline was safe and well tolerated, and was associated with better study retention than placebo.

Pilot Study 2: A 12-week, double-blind, placebo-controlled trial of citicoline add-on therapy in patients with BPD I disorder and cocaine abuse/dependence

Methods: 130 outpatients with BPD (depressed), cocaine dependence and a cocaine-positive urine at baseline were given citicoline or placebo add-on therapy to stable doses of mood stabilizers. Both groups received cognitive behavioral therapy and a contingency management plan of escalating payments for each urine sample provided. These payments were not related to whether the urine drug screen (UDS) was positive. **Results:** Among those with at least one post-baseline visit (n=60 citicoline, n=61 placebo) a group (f=4.5, df=1,1057, p=.0351) and group by time interaction (f=11.2, df=1,1057, p=.0009) was observed. Similar results were observed when imputing missing data as cocaine-positive [treatment group effect (p=.0222), treatment group by time effect (p=.0151)]. Completion rates non-significantly favored citicoline (71% vs. 57%).

In those with alcohol dependence, citicoline (n=33) showed a trend toward a greater decrease in days per week of alcohol use than placebo (n=37) (-3.67±4.11 days vs. -1.86±4.44 days, p=.084).

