3.3.b.13. Blood Levels of Choline and Neurosteroids: The blood draws for these analyses will be taken at baseline and at the final visit, and the final scheduled for approximately 3 hours after the last dose of study drug. Choline: Citicoline is rapidly hydrolyzed to the active metabolite choline following administration. As such, we propose using plasma choline as a study endpoint as in other studies.^{127, 128} Choline will be quantitated at Texas Tech University Health Sciences Center School of Pharmacy. The facility has extensive experience and specializes in analysis of drugs and metabolites contained in complex biologic matrices using mass spectrometry methods. A liquid chromatography-tandem mass spectrometry method will be transferred from the literature, developed, and validated for analysis. Choline will be extracted from plasma, and chromatographic separation will be carried out using a Shimadzu Nexera UHPLC system and reverse phase (RP) C18 column. Plasma choline content will be quantified using an AB Sciex 5500 QTRAP® in multiple reaction mode (MRM). Method development and validation will be completed in accordance with FDA Guidance for Industry, Bioanalytical Method Validation and contain studies to document (a) selectivity and specificity, (b) precision and accuracy, (c) linearity and lower limits of detection (LLOD), and (d) requisite stability studies. Choline calibration curves have been previously shown to be linear over a range of 0.05 - 5.0µg/mL with a limit of detection (LOD) of 0.025 µg/mL. Neurosteroids: We will obtain circulating serum levels of allopregnanolone, pregnenolone and pregNANolone as indicators of central neurosteroid levels. In animal models, serum neurosteroid levels appear to be closely related to hippocampal levels.¹²⁹ Neurosteroid levels in serum will be determined by the laboratory of [name] at Duke University using a highly sensitive and specific gas chromatography-mass spectrometry method as described previously.^{88, 130} One milliliter of serum will be extracted three times in ethyl acetate before high-pressure liquid chromatography purification using tetrahydrofuran, ethanol, and hexane in the mobile phase. Samples will be injected in duplicate. In prior work mean intra-assay coefficients of variation for pregnenolone and allopregnanolone were 0.9% and 2.9%,

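### Cognition and the SIP have one post-baseline measurement and no stated collection at early exit, so read literally their analysis is completers-only; the timing of closing labs, pregnancy test and blood levels is worded inconsistently

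*Combined protocol and SAP*

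**What the plan says.** **Cognition and SIP.** Section 3.3.b.1 states: "Cognition, including the domains of memory, decision making, impulsivity, attention, and executive functioning will also be assessed at baseline and week 12". In Table 2 the row "WHO-UCLA AVLT, TMT A and B, Stroop, SIP" is marked at the second baseline visit and in the last column, headed week 12 and final, and nowhere between. Under Statistical Methods in section 3.3.c, measures taken only at "baseline and week12 (e.g. cognitive assessments, neurosteroid and choline levels) will be analyzed using analysis of variance (ANOVA"). The SIP is not named there but has the same schedule.

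**Early leavers.** Section 3.3.b.5 gives the exit survey at week 12 or, for someone who stops early, at their last study visit. In the supplied text no other assessment has such a rule.

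**Closing labs and pregnancy test.** Section 3.3.b.8 says "At week 6 and at exit, participants will receive a repeat of the lab evaluation", with the pregnancy test repeated at the same times. Section 3.3.b.1 and Table 2 put both at weeks 6 and 12. Section 3.3.c analyses the liver enzymes and CDT at baseline and weeks 6 and 12.

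**Choline and neurosteroid levels.** Section 3.3.b.13 says "The blood draws for these analyses will be taken at baseline and at the final visit". Section 3.3.c says week 12.

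**Dropout.** Section 3.3.d expects completion above 70% overall, with no figure by arm. It plans local-influence, pattern-mixture and multiple-imputation sensitivity analyses for repeated measurements.

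**The concern.** A participant who leaves at week 4 or week 9 has no closing cognition or SIP value under the literal schedule, and TLFB-style recall cannot recover a missed memory test. An ANOVA of baseline and week 12 scores then compares only those who stayed.

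That matters for two reasons. Possible cognitive benefit is one of the stated grounds for testing both drugs (section 3.1.f). Leaving is also unlikely to be unrelated to the outcome: the discontinuation criteria in section 3.3.b.3 include worsening mood and symptoms that impair cognition. If citicoline also holds more participants in the study than placebo does, the two groups of completers are filtered to different degrees, and the comparison is no longer protected by randomization.

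The inconsistent wording for labs, pregnancy test and blood levels is a smaller matter. Two sites working from this text could differ on what to collect from someone who stops early.

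**Working it through.** **1. The plan's own figure.** Section 3.3.c states 81.4% power with 66 per arm at effect size 0.50, two-sided 5%. A two-sample t-test gives 81.35% and the normal approximation 81.9%, so the figure reproduces with all 66 evaluable and no allowance for dropout. It refers to the primary outcome. No power is stated for cognition or the SIP.

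**2. Missing closing values overall.** At the 70% floor: 199 × (1 − 0.70) = 59.7, or about 60 participants at most, since the plan expects more than 70%.

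**3. Retention by arm.**
- Citicoline: significantly better retention than placebo in two studies (section 3.1.f); more than twice the completion in Pilot 1, with no rates given; 71% against 57% in Pilot 2, not significant.
- Pregnenolone: similar to placebo in Pilot 4.

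**4. Completers and illustrative power.** Completers = n per arm × completion rate. Power is the t-test at effect size 0.50, borrowed from the primary outcome for illustration only. There are 66 per arm if three arms continue, and 33 + 50 = 83 per arm if one drug is retained.

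| n per arm | Completion (citicoline/placebo) | Completers | Power |
|---|---|---|---|
| 66 | all | 66 / 66 | 81% |
| 66 | 70% / 70% | 46 / 46 | 66% |
| 66 | 71% / 57% | 47 / 38 | 62% |
| 83 | all | 83 / 83 | 89% |
| 83 | 70% / 70% | 58 / 58 | 76% |
| 83 | 71% / 57% | 59 / 47 | 72% |

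The Pilot 2 rates average 64%, below the plan's forecast. Those rows are a separate scenario, not a refinement of step 2.

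**5. Possible selection bias with no true effect.** Assume a latent tendency to complete that correlates r with the outcome, equally in both arms. The completers' mean is shifted by r × φ(z)/p, where p is the completion rate and z the normal quantile of 1 − p.
- p = 0.71: φ(z)/p = 0.482. p = 0.57: 0.689. The difference is −0.207, which is −0.02 SD at r = 0.1 and −0.10 SD at r = 0.5.
- An assumed 90% against 45% (a twofold ratio, not in the documents): 0.195 − 0.880 = −0.685, which is −0.07 to −0.34 SD over the same range of r.
- Equal completion: zero.

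The values of r are assumptions. With positive r (those doing better stay), the shift works against citicoline; with negative r it works in its favour. If reasons for leaving differ between arms, this model does not give the direction.

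**The case against.** The strongest reply is that the text can be read to cover early leavers. The last column of Table 2 is labelled final as well as week 12, and the exit survey in that column is given at the last visit on early discontinuation. The sponsor also uses *exit* and *week 12* as synonyms: Pilot 4's levels are drawn at week 12 in its methods and reported as changes to exit in its results. This is fair. It means that completers-only is the literal reading, not a stated intention. It does not supply a rule for cognition, which sections 3.3.b.1 and 3.3.c place at week 12.

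Some stronger inferences are not supported:
- **That labs and the pregnancy test exist only for completers.** They also have a week 6 sample, and section 3.3.b.8 may cover exit.
- **That blood levels are fixed at week 12 only.** Section 3.3.b.13 says the final visit.
- **That the plan forecasts different completion in every arm.** It gives one overall figure. Better retention is a fair inference for citicoline only, and that arm may be dropped at the interim analysis.
- **That early leavers offer nothing to imputation.** They have baseline cognition and whatever weekly drinking, mood and craving data were collected before they left. The gap is that section 3.3.c does not link the methods of section 3.3.d to the ANOVA endpoints.

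An early-termination procedure may also stand in the Human Subjects section that section 3.3.b.9 cites, which is not in the supplied text.

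**Conclusion.** The point holds for cognition and the SIP. Each has one post-baseline measurement, no stated collection at early exit, and no missing-data method tied to its analysis. Read literally, up to about 60 of 199 participants have no closing value, and the citicoline comparison could be selected after randomization. Under the assumptions above the shift is 0.02 to 0.10 SD at Pilot 2's completion rates. It would be larger only with a much wider gap in completion and zero with none; its true size is unknown.

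For closing labs, pregnancy test and blood levels the finding is limited to inconsistent wording between sections.

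A reader might infer that the trial's main result is compromised. It is not: drinks per drinking day comes from the TLFB, scheduled at every visit, so the primary analysis does not depend on this point. This is a cheap improvement to secondary and exploratory endpoints.

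**What to change.** 1. In section 3.3.b.1 and Table 2, give cognition (AVLT, TMT, Stroop) and the SIP the timing rule already written for the exit survey: week 12, or the last study visit for those who stop early. Record weeks on study at that assessment.
2. In sections 3.3.c and 3.3.d, extend the multiple-imputation and pattern-mixture analyses to these endpoints, state how early-exit values enter, and show the completers-only result alongside.
3. Reconcile sections 3.3.b.1, 3.3.b.8, 3.3.b.13 and 3.3.c and Table 2 on when closing labs, the pregnancy test and blood levels are taken. If any levels are drawn at early exit, record time since last dose, because section 3.3.b.13 ties the final draw to about 3 hours after dosing. Whether to pool such levels with week 12 values is open to judgement.

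The cost is a table heading and a few sentences, and it reuses a visit the plan already foresees. There are two downsides. Early-exit scores reflect less than 12 weeks of treatment, some of it during titration, and some who leave will not attend a last visit, so missingness is reduced rather than removed.
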